9.3 Major Protocol Deviations

Population: Full Analysis Set

Target Phases: Core Phase, Extension Phase

Analysis Items:
- Major protocol deviations

Contents:
- Calculate the number of subjects and the percentages of those with and without major deviations from the protocol with their deviation contents.
- Denominator to calculate the percentage are below.

| Items | The denominator of percentage |
|--|---|
| Major Protocol Deviations (Yes/No) Deviation category | The number of subjects in Full Analysis Set |

- Deviation category is as below:
 - Safety
 - Informed Consent
 - Eligibility Criteria
 - Protocol Implementation
 - Investigational Products
 - Concomitant and Prohibited Medications or Non-Drug Therapy
 - General GCP Non-Adherence
 - Other
- Subjects with more than one major protocol deviation will be counted once for each category.
- Only major protocol deviations will be presented

9.4 Analysis Datasets

Population: Full Analysis Set

Target Phases: Core Phase, Extension Phase

Analysis Items:
- Analysis datasets

Contents:
- Calculate the number of subjects in the following population.
➤ Full Analysis Set (FAS)
➤ Per Protocol Set (PPS)/excluded from PPS
➤ Reasons for exclusion of PPS
➤ Safety Set (SAF)

10 Demographics and Baseline Characteristics

10.1 Demographics and Baseline Characteristics

Population: Safety Set

Target Phases: Core Phase, Extension Phase

Analysis items: - Refer to the table of Background Factors

Contents:
- Descriptive summaries of demographic and other baseline characteristics will be presented for the subjects in the Safety Set.
- For categorical data and ordinal data, calculate the number of subjects and percentages.
- For continuous data, calculate the descriptive statistics.

Definitions
- Unknown and Missing values: If unknown or missing values are observed, add “Unknown”/“Missing” category.
- For each item, the denominator is as below. Subjects of “Unknown”/“Missing” category are included in the denominator.

| Items | The denominator of percentage |
|------------------------|--------------------------------------|
| Childbearing potential | The number of female subjects |
| Others | The number of subjects in Safety Set |

[Background Factors]

| Classification [Unit] | Category |
|-----------------------|----------|
| Age (years) | <65, ≥65 |

| Classification [Unit] | Category |
|--|--|
| Sex | Male, Female |
| Childbearing potential *only for female | Yes, No |
| Race | Asian (Japanese) |
| Height (cm) | - |
| Weight (kg) | - |
| BMI (kg/m ²) | - |
| Medical history | Yes, No |
| Surgical history | Yes, No |
| Concomitant ITP medication at baseline ^a | Yes, No |
| Number of platelet transfusions in the previous 1 year | - |
| Number of previous hospitalizations for ITP | - |
| Number of previous significant bleeding events | - |
| Baseline platelet count ^b | $\leq 15 \times 10^9 / \text{L}$, $> 15 \times 10^9 / \text{L}$ |
| Splenectomy status | Yes, No |
| Baseline creatinine clearance ^c | $30 \leq - < 60 \text{ mL/min}$, $60 \leq - < 90 \text{ mL/min}$, $\geq 90 \text{ mL/min}$, Missing |

^a: Concomitant ITP medication at baseline is defined as medications with ATC level 2 = “CORTICOSTEROIDS FOR SYSTEMIC USE” that (1) start before the first dose of study drug and are continuing at the time of the first dose of study drug of Core Phase, or (2) start on the date of the first dose of study drug of Core Phase.

^b: Baseline platelet count is the average of the assessment of Screening Visit and Day 1 Baseline Visit. The average is recorded in the database and will be used directly.

^c: Baseline creatinine clearance is calculated by Cockcroft-Gault formula:

Male: $(140 - \text{Age (yrs)}) \times \text{weight (kg)} / (72 \times \text{creatinine (mg/dL)})$.

Female: $0.85 \times (140 - \text{Age (yrs)}) \times \text{weight (kg)} / (72 \times \text{creatinine (mg/dL)})$.

Age (yrs), weight (kg), creatinine (mg/dL) are taken at baseline.

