### **5.2** Exclusion Criteria

## **5.2.1** Primary Investigation Phase (Core Phase)

Subjects who meet any of the following criteria will not be eligible to participate in the study:

- 1. Subjects with known secondary immune thrombocytopenia (e.g., with known *Helicobacter pylori*-induced ITP, subjects infected with known human immunodeficiency virus [HIV] or HCV or subjects with known systemic lupus erythematosus).
- 2. Subjects with known inherited thrombocytopenia (e.g., MYH-9 disorders) or hereditary thrombophilic disorders (e.g., Factor V Leiden, antithrombin III deficiency).
- 3. History of myelodysplastic syndrome (MDS).
- 4. History of arterial or venous thrombosis.
- 5. Subjects with a history of significant cardiovascular disease (e.g., congestive heart failure [CHF] New York Heart Association Grade III/IV, arrhythmia known to increase the risk of thromboembolic events [e.g., atrial fibrillation], angina, coronary artery stent placement, angioplasty, coronary artery bypass grafting).
- 6. Subjects with a history of cirrhosis, portal hypertension, or chronic active hepatitis.
- 7. Subjects with concurrent malignant disease or receiving cytotoxic chemotherapy for a reason other than ITP treatment.
- 8. Use of immunoglobulins (IVIg and anti-D) or corticosteroid rescue therapy within 1 week of Day 1/Baseline.
- 9. Splenectomy or use of rituximab within 12 weeks of Day 1/Baseline.
- 10. Use of romiplostim or eltrombopag within 1 week of Day 1/Baseline.

- 11. Use of chronic corticosteroid treatment or azathioprine within 4 weeks of Day1/Baseline, unless receiving a stable dose for at least 4 weeks.
- 12. Use of mycophenolate mofetil, cyclosporin A, or danazol within 4 weeks of Day1/Baseline, unless receiving a stable dose for at least 12 weeks.
- 13. Use of cyclophosphamide or vinca alkaloid regimens within 4 weeks of Baseline Visit.
- 14. Currently receiving moderate or strong dual inhibitors/inducers of CYP2C9 and CYP3A4 (see Appendix D for examples).
- 15. Serum creatinine  $\geq 1.5 \times$  the upper limit of normal (ULN).
- 16. Serum bilirubin ≥2×ULN.
- 17. Alanine aminotransferase (ALT) or aspartate aminotransferase (AST)  $\geq 3 \times ULN$ .
- 18. Females who are pregnant (positive beta-human chorionic gonadotropin positive [β-hCG] test) or breastfeeding.
- 19. Known allergy to avatrombopag or any of its excipients.

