## 6.5.2 Allowed Medications and/or Procedures

Coronavirus Disease 2019 (COVID-19) vaccinations (and any other vaccinations) are allowed with no restrictions on the specific type. There will be no impact due to a vaccination on the study drug administration or the ability to enroll in the study. Any administered vaccine should be recorded as a concomitant medication.

Subjects should be instructed to contact site personnel before starting any new treatments. Treatments not specified as prohibited are permitted during the study.

Permitted ITP concomitant background therapies are as follows:

- Corticosteroids and/or azathioprine must be taken at a stable dose for 4 weeks before enrollment
- mycophenolate mofetil, cyclosporin A, or danazol must be taken at a stable dose for at least 12 weeks before enrollment

At the discretion of the Investigator, subjects will be allowed to use aspirin, other salicylates, or approved adenosine diphosphate (ADP) receptor antagonists, (e.g., clopidogrel, prasugrel) during the study once their platelet count has risen.

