# 6.5.4 Rescue Therapy

Subjects will be allowed to receive rescue therapy at the discretion of the Investigator or Sub-Investigator based on their clinical assessment. Rescue therapy should be considered if there is an urgent need to increase platelet count for example:

- Life-threatening thrombocytopenia, such as a platelet count  $<10\times10^9/L$
- Major bleed
- Clinical signs or symptoms suggesting potential bleed (i.e., wet purpura)

Rescue therapy will be defined as the addition of any new ITP medication or medication to treat thrombocytopenia (examples below). TPO receptor agonists are not allowed as rescue therapy.

- Corticosteroids
- Intravenous immunoglobulin (IVIg) therapy
- Anti-D therapy
- Mycophenolate mofetil
- Azathioprine
- Danazol
- Cyclosporin A
- Platelet transfusion
- Any increase in baseline dose of a concomitant ITP medication

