11.3.9 Subjects with any Rescue Therapy Use

Population: Full Analysis Set, Per Protocol Set (for Core Phase only)

Target Phases: Core Phase, Extension Phase

Analysis items: - Rescue therapy (Yes/No)

Contents: - The number of subjects with rescue therapy (Yes/ No) and its proportion with 95% CI are calculated.

Definitions: - Rescue therapy (Yes): The number of subjects who use at least one rescue therapy after the first administration of study drug in each phase (Core Phase (26-week treatment period) or Extension Phase).

- If one subject takes the same therapy in both Core Phase and Extension Phase (e.g. the end date of rescue therapy in Core Phase is ongoing), that subject will be counted in Core Phase and Extension Phase respectively.
- The denominator to calculate the proportion is the target population (the number of subjects in Full Analysis Set/Per Protocol Set)
- Rescue therapy will be defined as the addition of any new ITP medication or medication to treat thrombocytopenia (examples below). TPO receptor agonists are not allowed as rescue therapy.

- Corticosteroids (ATC level 2 = “CORTICOSTEROIDS FOR SYSTEMIC USE”)
- Intravenous immunoglobulin (IVIg) therapy (ATC level 2= “IMMUNE SERA AND IMMUNOGLOBULINS”)
- Anti-D therapy (PT = “Anti-D (rh) immunoglobulin”)
- Mycophenolate mofetil (PT = “Mycophenolate mofetil”)
- Azathioprine (PT = “Azathioprine”)
- Danazol (PT = “Danazol”)
- Cyclosporin A (PT = “Ciclosporin”)
- Platelet transfusion (concomitant procedure as “TRANSFUSIONS”)
- Any increase in baseline dose of a concomitant ITP medication
- Regarding 95% CI for binomial proportions, refer to [8.3.2 Proportion and Confidence Intervals for proportions.](#)

11.3.10 Subjects with a Reduction/Discontinuation in use of Concomitant ITP Medications from Baseline

Population: Full Analysis Set, Per Protocol Set

Target Phases: Core Phase

Analysis items: - Reduction in use of concomitant ITP medications

- Discontinuation in use of concomitant ITP medications

Contents: - Calculate the number of subjects who have a reduction/discontinuation of Concomitant ITP medications after baseline.

For each item, the denominator is as below

| Items | The denominator of percentage |
|--|---|
| 
 • Reduction of Concomitant ITP medications after baseline • Discontinuation of Concomitant ITP medications after baseline | The number of subjects who used concomitant ITP medications at baseline |

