Definitions: ITP medications are defined as the medications with ATC level 2 = “CORTICOSTEROIDS FOR SYSTEMIC USE”

Baseline ITP medications are defined as the ITP medications that are taken on the day of first administration; and concomitant ITP medications use at Core Phase are defined as ITP medications that start after the day of first administration and up to the last day of 26-week treatment period (excluding dose-tapering period) of Core Phase.

Only subjects with use of concomitant ITP medications at baseline will be included in the analysis. If a subject has use of concomitant ITP medication at baseline and has all post-baseline total daily doses for same medications (by PT) reduced without later increasing to the baseline or higher dose, or has no use of concomitant ITP medication post-baseline during 26-week

treatment, this subject is considered as having a reduction in use of concomitant ITP medication from baseline.

Subjects who discontinue all concomitant ITP medications before the last dose date of 26-week treatment will be considered as having a discontinuation of concomitant ITP medications.

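### The SAP classes any systemic corticosteroid started on the first-dose date as baseline ITP medication, contrary to the protocol, so a short Day 1 course would score as a discontinuation of background therapy

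*SAP*

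**What the plan says.** **Baseline flag.** SAP 10.1, footnote a, identifies baseline concomitant ITP medication by one ATC level 2 class, systemic corticosteroids. A drug qualifies if it began earlier and was continuing at the first dose, "or (2) start on the date of the first dose of study drug of Core Phase".

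**Discontinuation endpoint.** SAP 11.3.10 has its own definition: "Baseline ITP medications are defined as the ITP medications that are taken on the day of first administration". The denominator is the subjects with such use at baseline. A subject who stops all of it before the last dose date of the 26 weeks counts as having discontinued. No minimum prior use is required.

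**Protocol, background therapy.** Section 6.5.2 states: "Corticosteroids and/or azathioprine must be taken at a stable dose for 4 weeks before enrollment". Exclusion 11 in 5.2.1 bars chronic corticosteroid within 4 weeks of Day 1 unless the dose has been stable for at least 4 weeks. Exclusion 8 bars "Use of immunoglobulins (IVIg and anti-D) or corticosteroid rescue therapy within 1 week of Day 1/Baseline".

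**Protocol, rescue.** Section 6.5.4 states: "Rescue therapy will be defined as the addition of any new ITP medication or medication to treat thrombocytopenia". Corticosteroids head its list of examples.

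**SAP, rescue.** Section 11.3.9 repeats the protocol's definition and counts subjects who "use at least one rescue therapy after the first administration of study drug in each phase". For the primary endpoint, 11.1.1 makes every day after the rescue start date a nonresponse. For Day 8, 11.2.1 makes a subject with rescue at any time up to and including that visit a nonresponder.

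**The concern.** A steroid newly started for ITP on Day 1 cannot be permitted background therapy under the protocol, yet two SAP definitions put it on the baseline side. SAP 11.3.10 reinforces this by treating as on-study ITP medication only what starts after the day of first administration. SAP 11.3.9 draws its line at the first administration itself. A steroid taken on Day 1 after the study dose is therefore baseline under two sections and rescue under a third. No rule of precedence is given. Protocol 6.5.6 names dates, indication and dose for the eCRF, but not clock times.

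Two consequences follow directly. The discontinuation endpoint is meant to show background therapy being withdrawn: Protocol 6.5.3 speaks of subjects receiving the medication when they enter the study. As written, it can be met by a few-day course with no background behind it. The baseline table also describes that subject as a background-therapy user.

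A third consequence is conditional. If the programming lets the baseline label displace the rescue label, later counts of at least 50×10⁹/L would be credited in the primary and Day 8 analyses.

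**Working it through.** **1. How a corticosteroid started on Day 1 is classed**

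| Rule | Class |
|---|---|
| SAP 10.1, footnote a, clause (2) | Baseline ITP medication, whatever the indication |
| SAP 11.3.10 | Baseline ITP medication, whatever the indication |
| Protocol 6.5.2 and exclusion 11 | Not permitted background: no 4 weeks of stable dose |
| Protocol 6.5.4 | Rescue, if newly added for ITP |
| SAP 11.3.9 | Rescue, if new for ITP and used after the first study dose |
| SAP 11.1.1 and 11.2.1 | Nonresponse afterwards, if it is rescue; footnote a is not cited |

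The first two rows conflict with the protocol whatever the programmer does. The last two rows work as intended once the drug is identified as rescue.

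**2. Effect on 11.3.10**

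The number of subjects on baseline steroids is not given, so these counts are assumptions. One short-course Day 1 starter changes k/b to (k+1)/(b+1):

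- 0/3 = 0% becomes 1/4 = 25%
- 1/5 = 20% becomes 2/6 = 33%
- 2/8 = 25% becomes 3/9 = 33%
- 4/12 = 33% becomes 5/13 = 38%

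**3. Conditional effect on Day 8 and the primary endpoint**

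Inputs from SAP section 6: mean 12.0 weeks, SD 8.75, hurdle 8.02, n = 19. The plan's sample size reproduces with the normal formula: (1.96 × 8.75 / (12.0 − 8.02))² = 18.57, rounded up to 19. No figure in the documents depends on the footnote.

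Suppose one of the 19 is a Day 1 starter who is credited as baseline when the protocol makes the drug rescue.

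- Day 8 rate: 1/19 = 5.3 percentage points.
- Primary mean: a subject responding from Day 8 to Day 182 scores (182 − 8 + 1)/7 = 25 weeks, or 0 if classed as rescue. The mean moves by 25/19 = 1.32 weeks. Smaller losses move it by 4/19 = 0.21 or 12/19 = 0.63.

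Lower 95% limit by the t interval (SAP Appendix 1 uses PROC TTEST; t with 18 df = 2.101), with SD 8.75 before the change and the SD recomputed after it:

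| Observed mean | Limit before | 4 weeks lost | 12 weeks lost | 25 weeks lost |
|---|---|---|---|---|
| 12.0 | 7.78 | 7.45 | 6.95 | 6.56 |
| 13.0 | 8.78 | 8.44 | 7.91 | 7.48 |
| 14.0 | 9.78 | 9.43 | 8.88 | 8.40 |

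At 12.0 the hurdle is missed both before and after, so no decision changes. At 13.0 a loss of 12 weeks or more takes the limit below 8.02. At 14.0 the hurdle is met throughout. One subject can therefore change the result only when the observed mean is not far above the break-even value, 8.02 + 2.101 × 8.75/√19 = 12.24.

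**The case against.** A reader might infer that footnote a lets a steroid-driven response be credited to avatrombopag. The documents do not support that. The footnote defines a row of a baseline table and takes nothing off the rescue list. The limit in 11.3.9 to use after the first administration belongs to the subject count for that table; the definition of rescue is a separate item without it. Under 11.2.1 the order of steroid and study drug on Day 1 is irrelevant, and under 11.1.1 a Day 1 rescue start makes every later day a nonresponse. Misplaced credit needs a further programming choice that the SAP does not prescribe. This part of the objection stands.

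Identification is also partly handled. Sites record rescue use from Visit 3 (Protocol 7.2.2), indication is captured (6.5.6), and SAP section 14 lists rescue therapy separately from concomitant ITP medication. Eligibility is rechecked at Visit 2, and deviations are reported.

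Nor is every Day 1 steroid either rescue or an eligibility violation. Protocol 6.5.2 says: "Treatments not specified as prohibited are permitted during the study". A short course for another indication may be neither. This stands too and limits the fix: reclassifying on ATC code alone could make such a subject a nonresponder for the whole treatment period.

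The 11.3.10 effect comes from that section's own definition, not from footnote a, and it concerns a descriptive endpoint. The subgroup sections do not cite the footnote, so that link is likely but inferred.

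None of this removes the conflict with the protocol's stable-dose condition, the false discontinuation, or the missing same-day rule.

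**Conclusion.** The point holds as an inconsistency in definitions. SAP 10.1 clause (2) and SAP 11.3.10 admit as baseline ITP medication a steroid that the protocol does not accept as background therapy. The certain effects are on 11.3.10 and the baseline table. One such subject adds 1 to both numerator and denominator of the discontinuation rate, which is 8 points in the assumed 2/8 case and more with fewer users. The subject probably also moves into the concomitant-medication subgroup of 11.1.2, 13.2.2 and 13.2.5.

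The primary and Day 8 analyses are exposed only through the unsettled classification of a same-day start. The possible shift per subject is 5.3 points at Day 8 and at most about 1.3 weeks in the primary mean. That maximum assumes uninterrupted response from Day 8 to Day 182, and nothing in the documents shows that such a subject exists. The hurdle calculations are illustrations, not predictions.

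**What to change.** 1. SAP 10.1, footnote a: delete clause (2).
2. SAP 11.3.10: require that a baseline ITP medication was given for ITP, started before the first-dose date, and meets the protocol's stable-dose period. Use the same definition for the baseline row, and cite it in the subgroup sections.
3. SAP 11.3.9: state that an ITP-indicated medication newly started on the first-dose date is analysed as rescue from that date and not as baseline. State that steroids given for other indications are not reclassified.

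Settle this before Core Phase database lock. In an open-label, single-arm trial of 19 subjects, a choice made after seeing the records would be data-dependent.

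The cost is small wording and programming work. Indication and dates are already collected, so no new data are needed. If such a subject exists, the result may be slightly less favourable.

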10.2 Medical History

Population: Safety Set

Target Phases: Core Phase

Analysis items: - Medical History

Contents: - For medical history (Yes/No), calculate the number of subjects and percentages.
- For medical history terms, calculate the number of subjects and percentages by Preferred term (PT) with MedDRA.
- If there are multiple records with the same PT in the same subject, count one record per subject.
- The number of subjects and percentages by PT ordered by decreasing frequency.

Definitions: For each item, the denominator is as below

| Items | The denominator of percentage |
|--|--------------------------------------|
| Medical history (Yes/No) PT (Medical history) | The number of subjects in Safety Set |

10.3 Concomitant Medication

Population: Safety Set

Target Phases: Core Phase, Extension Phase

Analysis items: - Concomitant medication

Contents: - Concomitant medications are displayed with ATC level 2 and preferred name.
- For Concomitant medication, calculate the number of subjects and percentages by ATC2 and preferred name with WHO Drug.
- If there are multiple records with the same code in the same subject, count one record per subject.

Definitions:

- Prior medications (Core Phase)
Defined as medications that stop prior to the first dose of study drug of Core Phase.
- Concomitant medications (Core Phase)
Defined as medications that (1) start before the first dose of study drug and are continuing at the time of the first dose of study drug of Core Phase, or (2) start on or after the date of the first dose of study drug of Core Phase, up to 30 days after the last dose of study drug during the Core Phase (and before the first dose of Extension Phase if subject continues into the Extension Phase).
- Concomitant medications (Extension Phase)
Defined as medications that start on or after the first day of Extension Phase and up to the last day of treatment period of Extension Phase.

For each item, the denominator is as below

| Items | The denominator of percentage |
|---|--------------------------------------|
| Subjects with at least one concomitant medication | The number of subjects in Safety Set |
| ATC level 2 | |
| Preferred name | |

11 Efficacy Analyses

All analyses of platelet counts will be based on local laboratory results.

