## 3.3 Other Efficacy Endpoints

Other efficacy endpoints include the following:

- Durable platelet response as defined by: proportion of subjects who have at least 6 of 8 (i.e., ≥75%) weekly platelet counts ≥50×10^9/L during the last 8 weeks of treatment over the 26-week treatment period in the absence of rescue therapy
- Incidence and severity of bleeding symptoms associated with ITP, including bleeding, bruising, and petechiae, measured using the WHO Bleeding Scale
- Maximum duration (in weeks) of continuous response for each subject
- Proportion of subjects receiving rescue therapy during the 26-week duration of the study
- Proportion of subjects with a discontinuation in use of concomitant ITP medications from baseline
- Complete responder by International Working Group (IWG) definition: platelet count ≥100×10^9/L and absence of bleeding (Rodeghiero, 2009)
- Responder by IWG definition: platelet count  $\ge 30 \times 10^9 / L$  and at least a 2-fold increase in baseline count and absence of bleeding (Rodeghiero, 2009)

Additionally, in the Extension Phase, effectiveness will be assessed by measuring platelet counts, reduction in use of concomitant ITP medication, and bleeding events. Specifically,

- Median platelet count of all subjects at selected time points (monthly)
- Proportion of subjects needing rescue therapy
- Incidence and severity of bleeding (in accordance with the WHO Bleeding Scale)

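### The SAP's Extension Phase concomitant medication table counts only drugs that start in the Extension, so it omits any drug continuing from the Core Phase

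*SAP*

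**What the plan says.** SAP 10.3 lists "Target Phases: Core Phase, Extension Phase" for the concomitant medication summary. Its rows are the subjects with one or more such medications, then ATC level 2 classes, then preferred names. The denominator is the Safety Set.

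The Core Phase definition has two limbs. The first takes in medications that "start before the first dose of study drug and are continuing at the time of the first dose of study drug of Core Phase". The second takes in those starting on or after first dose. It closes 30 days after the last Core dose, and before the first Extension dose for subjects who continue.

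The Extension Phase definition has a single limb: "Defined as medications that start on or after the first day of Extension Phase", with a cut-off at the end of Extension treatment. Only the start date decides.

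SAP 11.3.9 handles rescue therapy that spans the two phases differently: "that subject will be counted in Core Phase and Extension Phase respectively".

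**The concern.** Concomitant ordinarily means taken alongside study drug, whenever the drug was begun. The Core rule follows that meaning and the Extension rule does not. A subject who takes the same steroid throughout the Extension and starts nothing new would count as having no concomitant medication in that phase.

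The protocol makes carry-over foreseeable:

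- Background ITP therapy is allowed at entry. Protocol 6.5.2 says "Corticosteroids and/or azathioprine must be taken at a stable dose for 4 weeks before enrollment", and it makes similar provision for mycophenolate mofetil, cyclosporin A and danazol.
- Protocol 6.5.3 confines downward titration of these drugs in the Core Phase to Visits 8 to 13, and Protocol 4.3.4 bars it in the Maintenance Period except for a safety concern. A subject still on background therapy after Visit 13 will often be on it at Extension entry.
- Protocol 4.4 and 7.3.1 set extra visits for Extension subjects whose concomitant ITP medication is reduced, which presupposes that some are still taking it.
- Protocol 6.5.2 also allows aspirin and ADP receptor antagonists at the investigator's discretion (6.5.1 bars chronic use beyond 4 weeks in the Core Phase). One started late in the Core Phase and continued would be missed too.

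The Extension's primary objective is long-term safety, and bleeding and thromboembolic events are of special interest. Readers will want to know what else subjects were taking in that phase.

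**Working it through.** The point turns on a classification rule. The plan states no figure to reproduce, so the check applies the rules as written to test records.

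**Inputs.** The two definitions come from SAP 10.3. The dates are assumptions for illustration: first Core dose on day 1, first Extension day on day 183, last Extension treatment day on day 900. The seven medication records are invented.

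**Rules**, with S the start day and E the stop day:

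- Core: (S < 1 and E ≥ 1), or 1 ≤ S < 183.
- Extension as written: 183 ≤ S ≤ 900.
- Extension with an ongoing limb: 183 ≤ S ≤ 900, or (S < 183 and E ≥ 183).

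| Record | S | E | Core | Extension as written | Extension with ongoing limb |
|---|---|---|---|---|---|
| Steroid from before Core, ongoing | -200 | ongoing | yes | no | yes |
| Steroid started in Core, ongoing | 60 | ongoing | yes | no | yes |
| Steroid from before Core, stopped in Extension | -200 | 300 | yes | no | yes |
| Antihypertensive, ongoing | -900 | ongoing | yes | no | yes |
| New drug in Extension | 250 | 260 | no | yes | yes |
| Steroid stopped in Core | -200 | 100 | yes | no | no |
| Dose change entered as a new record in Extension | 220 | ongoing | no | yes | yes |

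The first four rows are carry-over drugs. As written, 0 of 4 count in the Extension; with the ongoing limb, 4 of 4 do. The steroid stopped in the Core Phase stays out under both rules, as it should. The last row shows a side effect of the current rule: a continuing drug is counted if a dose change is entered as a new record and missed if it is not, so data-entry practice affects the table.

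**Size in the table.** Let M be the number of Extension entrants in the Safety Set and k the number whose only Extension medications are carry-over drugs. The top row is too low by k/M. A per-drug row is too low by the share of subjects who continue that drug without a new record. The documents give neither M nor k, so k/M can lie anywhere from 0 to 1. For scale only: if all of about 19 planned subjects (Protocol 4.1) entered, each such subject would lower the top row by 1/19 = 5.3 percentage points.

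**Does another Extension summary fill the gap?**

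- SAP 10.1 repeats the demographics table for the Extension with a row for ITP medication at baseline. It covers systemic corticosteroids only and is tied to use "continuing at the time of the first dose of study drug of Core Phase, or (2) start on the date of the first dose" in the Core Phase, not to use at Extension entry.
- SAP 11.3.9 covers rescue therapy only.
- SAP 11.3.10, on reduction or discontinuation of ITP medication, is for the Core Phase only.
- SAP 13.2.2 and 13.2.5 split adverse events by use of concomitant ITP medications, including for the two phases combined. They do not tabulate which drugs were taken in the Extension.

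None of these shows background medication in use at or after Extension entry.

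**The case against.** Several points on the other side have force.

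*No data are lost.* A carried-over drug is counted in the Core table. Listings 16.2.4.5 and 16.2.4.7 cover both phases by subject, and with about 19 subjects a listing is a practical source. This stands: the gap is in the Extension summary, not in the database.

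*Results will not simply be read as monotherapy.* A reader might infer that the Extension outputs would present subjects on continuing steroids as free of ITP medication. The documents do not support this. The 10.3 table has no row for absence of ITP therapy, the Extension demographics still show who was on steroids at Core baseline, and the adverse event tables are split by ITP medication use.

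*SAP 11.3.9 is not a contradiction.* A reader might see a conflict between its carry-over rule and 10.3. It governs a separate endpoint with its own table, and the two rules can coexist. It also narrows the gap, since a rescue steroid still running at Extension entry appears in the Extension rescue table. It remains useful as a precedent for counting across phases.

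*The start-date rule may be deliberate.* The second Core limb ends before the first Extension dose, so each new start is assigned to one phase. The Extension table may have been meant to show new starts only. The documents state no such intent. If that is the aim, the table's label and top row describe it wrongly, and it is not comparable with the Core table, which includes ongoing drugs.

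*Carry-over may be small.* Protocol 6.5.3 allows background ITP drugs to be tapered and eliminated in the Core Phase. That is possible for ITP drugs but does not touch other long-term medication.

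**Conclusion.** The point holds on the plain text. The Extension rule in SAP 10.3 lacks the ongoing limb that the Core rule has, and the resulting table omits every drug continued unchanged from the Core Phase. The number of subjects affected is unknown and could be none or all entrants; no particular share can be drawn from the documents.

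The consequence is limited to one descriptive Extension summary. The primary endpoint, its hurdle, the sample size and the other efficacy endpoints are unaffected. The conclusion assumes that the definition is programmed as written and that a continuing drug keeps its original start date in the database.

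A neighbouring matter should be kept separate. Protocol 3.3 says that in the Extension "effectiveness will be assessed by measuring platelet counts, reduction in use of concomitant ITP medication, and bleeding events", while SAP 3.3.3 names rescue therapy in place of medication reduction. An ongoing limb in 10.3 would show who was taking what, but it would not measure reduction.

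**What to change.** In SAP 10.3, define Extension Phase concomitant medications as those that (1) started before the first Extension dose and are continuing at that dose, or (2) start on or after the first Extension dose, up to the last day of Extension treatment. This mirrors the Core definition and follows the same approach to carry-over as 11.3.9. It also makes the first Extension dose the common boundary, since the second Core limb already closes there. A drug spanning both phases will then appear in both tables, which is intended because each table describes its own phase.

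If a table of new starts is also wanted, give it separately and title it as such.

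The cost is one sentence in the SAP and one added condition in the program. It needs no new data and no change to the protocol or to any other analysis. It should be in place before any Extension table is run, including those produced when the last subject completes the Core Phase.
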